5.1.3. Last Participation Day

Last Participation Day = Last Participation Date – Reference Start Date

Note: Last Participation Day is used as the censor day for Kaplan-Meier analysis.

5.1.4. Study Day

Study Day = Current Date – Reference Start Date

5.2 Visit Windows

An assessment is considered scheduled if the assessment is identified by a nominal visit name (e.g., “Discharge”, “30 day”, and “1 year”) regardless if the actual visit date is within the protocol defined visit window. An assessment is considered unscheduled if no nominal visit name is identified. Unless specified, measurements collected from unscheduled assessments should be excluded from analyses. Disposition status will be summarized using occurrence date instead of nominal visit.

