4.4 Patient Treatment

Patients will be treated according to standard of care at their medical facilities and no additional tests or procedures will be performed.

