4.5 Data Collected

Routine clinical (such as Medical History, Risk Factors, Medication, Clinical Status, Procedure Information and Safety data) and echocardiographic data available from clinical records will be collected for the following time points:

- Baseline: pre-procedural data
- Procedural data: data collected as part of the procedure
- Discharge data: data collected prior to discharge from hospital
- 30 day visit: visit performed between discharge and up to 2 months post procedure
- 1 year follow up: visit performed between 10 months and 14 months post procedure

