5.1.2. Last Participation Date

The last participation date is defined as the latest date assessed with any available information concerning the patient (e.g., latest date out of: baseline assessment, procedure, discharge, follow-up visit, unscheduled visit, echo data, laboratory tests collection, study exit when exit reason is not lost to follow-up, and adverse event occurrence).

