8.3 Secondary Measures

Safety Measures

All AEs and SAEs with onset on or after the procedure date (Day 0) will be summarized using type of event by early events (≤ 30 days) and late events (> 30 days). Summaries of incidence rates (counts and percentages) will be prepared, where data is available.

Functional and Quality of Life Measures

Quality of Life (QoL) as measured by EQ-5D and KCCQ, will be scored according to algorithms provided by the vendor. The various summary scores produced by the algorithms will be analyzed as continuous variables. EQ-5D and KCCQ overall summary scores, and their changes from baseline to 30 days and 12 months will be summarized. Patients that are missing a baseline or follow up values will be excluded from the analysis.

 Edwards	Revision Date: August 22, 2019		Rev	1.0	For Use Only by Affiliates of Edwards Lifesciences	Page 13 of 13
	Title	Statistical Analysis Plan for PASCAL Registry				

Count and percentage of patients in each NYHA Class will be summarized. Change from baseline will be presented as a shift from baseline to 30-day and 12-month follow-up. Patients that are missing baseline or follow-up values will be excluded from the paired analysis.

Summary statistics, including mean, median, SD, and sample size, for 6MWT will be presented. Change in 6MWT at 30 days and 12 months over baseline will be summarized. Patients that are missing baseline or follow-up values will be excluded from the paired analysis. Patients unable to perform the walk due to a medical reason will be considered to have walked a distance of 0 m.

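### SAP 5.2 assigns MR grade, NYHA, 6MWT and QoL to visits by name alone, with no fallback for an unnamed value inside the protocol's date window

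*SAP*

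**What the plan says.** SAP 5.2 classifies an assessment by its label. A named visit counts "regardless if the actual visit date is within the protocol defined visit window". For the rest, "An assessment is considered unscheduled if no nominal visit name is identified", and the consequence follows: "Unless specified, measurements collected from unscheduled assessments should be excluded from analyses".

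The protocol works by date. Section 4.5 gives "1 year follow up: visit performed between 10 months and 14 months post procedure", and sets the 30-day visit as one performed from discharge up to 2 months. Section 4.4 states: "Patients will be treated according to standard of care at their medical facilities and no additional tests or procedures will be performed". Data come from routine records, retrospective collection is allowed (Protocol 3.1), and sites are asked to obtain source documents from outside facilities (Protocol 4.6).

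SAP 8.2 summarises MR severity by count and percentage. SAP 8.3 summarises EQ-5D, KCCQ, NYHA and 6MWT at 30 days and 12 months. Neither mentions unscheduled assessments. SAP 6.2 restricts endpoint analyses to patients with the required data available.

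Three items go by date instead. For disposition, "Disposition status will be summarized using occurrence date instead of nominal visit". Adverse events are split at 30 days from onset ("All AEs and SAEs with onset on or after the procedure date (Day 0) will be summarized using type of event"). The last participation date is the "latest date out of: baseline assessment, procedure, discharge, follow-up visit, unscheduled visit, echo data" and other contacts.

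**The concern.** The two documents identify a visit differently. Under the protocol, a routine echo at month 11 is a 1-year value because of its date. Under the SAP, it is a 1-year value only if someone gave it that name. Where the name is missing and the patient has no other value for that visit, the SAP excludes a measurement that meets the protocol's own definition, and the available-case rule then removes the patient.

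This matters more here than in a trial with study-ordered tests. Routine, retrospective and outside-facility records need not arrive with a registry visit name, so someone has to assign one, and neither document says how. Inclusion in a primary measure can then depend on a data-entry choice that the plan does not govern. The registry tests no hypotheses, so the percentages and their denominators are its main product.

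**Working it through.** **Does the text lead to exclusion?** Take a patient whose only echo after discharge is at month 11, entered without a visit name.

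1. Protocol 4.5: month 11 lies between 10 and 14 months, so the date meets the 1-year definition.
2. SAP 5.2: there is no nominal name, so the assessment is unscheduled and is excluded unless an exception is specified.
3. SAP 8.2: no exception for MR grade. SAP 8.3: none for NYHA, 6MWT or QoL.
4. SAP 6.2: no available value, so the patient leaves the 12-month percentage. The censoring sentence in SAP 6.2 concerns withdrawal and loss to follow-up; this patient is neither.

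**How large could it be?** The plan states no figure to reproduce. Every input below is an assumption except 200, the planned minimum enrolment. For simplicity all 200 are taken to have some in-window echo.

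- u = share of those patients whose only in-window echo is unnamed: 5%, 10%, 20%
- p₁ = MR ≤2+ among named echoes: 90% or 95%
- p₂ = MR ≤2+ among unnamed echoes: from 60% up to p₁

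The SAP rule reports p₁. Using all in-window data gives (1 − u)p₁ + u·p₂. The difference is u × (p₁ − p₂).

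| u | p₁ | p₂ | SAP 5.2 | All in-window | Difference |
|---|---|---|---|---|---|
| 5% | 90% | 60% | 171/190 = 90.0% | 177/200 = 88.5% | 1.5 points |
| 10% | 90% | 60% | 162/180 = 90.0% | 174/200 = 87.0% | 3.0 points |
| 20% | 90% | 60% | 144/160 = 90.0% | 168/200 = 84.0% | 6.0 points |
| 20% | 95% | 60% | 152/160 = 95.0% | 176/200 = 88.0% | 7.0 points |
| 10% | 90% | 80% | 162/180 = 90.0% | 178/200 = 89.0% | 1.0 point |
| 20% | 90% | 90% | 144/160 = 90.0% | 180/200 = 90.0% | 0 |

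With p₂ = 80% the full range is 0.05 × 10 = 0.5 to 0.20 × 15 = 3.0 points. If unnamed echoes were better than named ones, the sign would reverse.

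**Precision alone.** With p₁ = p₂ = 90% and u = 20%, the exact binomial 95% interval (the method in SAP 6.1) is 85.0% to 93.8% with n = 200 and 84.3% to 94.2% with n = 160. The width goes from 8.8 to 9.9 points.

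**The case against.** The strongest reply is that the case may hardly arise. Because the protocol windows are broad, a site following Protocol 4.5 would enter a month-11 echo as the 1-year visit. Validation queries (Protocol 5.1) and monitoring (Protocol 9.1) exist to correct entry errors, and analysing nominal visits only is a recognised, pre-specified choice. This stands as far as frequency goes: the number affected could be near zero. It does not remove the gap, because no labelling rule is written, both checks are worded as possible rather than certain, and a source record need not show a registry visit name. If every visit is labelled, the fallback changes nothing.

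Three stronger readings are tempting, and the documents do not support them.

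- *Every measurement is lost.* The exclusion carries an exception clause, and adverse events, disposition and last participation date are handled by date. Nothing suggests that the event-based primary safety measure is touched.
- *The excluded values are selectively symptom-driven, so the result leans upwards.* Neither document says why unscheduled assessments occur. With no tests ordered by the registry, named assessments may also be prompted by symptoms.
- *SAP 5.1.2 contradicts SAP 5.2 by counting unscheduled visits and echo data.* It does not. Any evidence of contact properly extends the censor day; which measurement represents a visit is another question.

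It is also fair to say that a fallback leaves the other half of SAP 5.2 alone: a named value from outside the window would still take precedence over an unnamed one inside it. That is a separate weakness of the same rule.

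**Conclusion.** The point holds in a limited form. As written, SAP 5.2 can exclude a value that meets the protocol's date definition and is the patient's only one for that visit. The measures exposed are MR grade (the primary performance measure), NYHA, 6MWT and QoL.

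The size is unknown. It is zero bias with some loss of precision if unnamed values resemble named ones. It is about 1.5 to 7 points of overstatement on the assumed inputs of 5% to 20% affected and 60% MR ≤2+ in unnamed echoes, and less for a smaller gap. A reader might take those points as an established upward bias; they are not, since neither the share affected nor the difference in outcome can be obtained from the documents. With no hypothesis tests, the effect is on reported percentages and denominators, not on error rates. It is a cheap improvement worth making, not a flaw that undermines the registry.

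**What to change.** In SAP 5.2, add: if no named assessment exists for a visit, the unscheduled assessment inside the protocol window closest to Day 30 (or Day 365) is used for that visit; state a tie-break, for example the later of two equally close values. Apply this to MR grade, NYHA, 6MWT and QoL. Report how many values are assigned this way for each measure and visit, and give the nominal-visit-only result as a sensitivity analysis.

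The cost is a few lines of SAP text and minor programming, with no new data collection. The small downside is that some substituted values may have been prompted by symptoms; comparing the two results will show whether they matter.

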6. STATISTICAL ANALYSIS

6.1 General Conventions

 Edwards	Revision Date: August 22, 2019		Rev	1.0	For Use Only by Affiliates of Edwards Lifesciences	Page 9 of 13
	Title	Statistical Analysis Plan for PASCAL Registry				

- For continuous variables, summary statistics will include mean, median, standard deviation (SD), IQR, sample size, minimum, and maximum. If confidence limits are desired, they will be computed using the t-distribution or normal approximation.
- For ordinal data, the count and percentage of patients will be presented.
- For categorical and qualitative variables, summaries will include the count and percentage of patients who are in the particular category. If confidence limits are needed, they will be computed using the exact binomial distribution.
- Time-to-event variable summaries will include the number of events, the number of patients with the event and Kaplan-Meier estimates at given time points. Standard errors will be calculated using Greenwood's formula and SAS defaults will be used for confidence bands and transformations on $S(t)$ for the confidence limits. Kaplan-Meier event rate plots will be presented via the cumulative hazard rate plotted against the days from implantation.
- All analyses will be performed using SAS® Software version 9.4 or later (SAS Institute¹, Inc., Cary, NC), unless otherwise specified.

6.2 Handling of Missing Data

All statistical analysis on the endpoints will be performed using only those patients with available data required for endpoint analysis.

Partial onset event dates are imputed for safety data using the result in the earliest event date possible. This imputation will only be performed as needed such as date variable is used in the variable derivation. However, no imputed dates will be presented in the listings.

 Edwards	Revision Date: August 22, 2019		Rev	1.0	For Use Only by Affiliates of Edwards Lifesciences	Page 10 of 13
	Title	Statistical Analysis Plan for PASCAL Registry				

- If the adverse event year is unknown, then the date will be imputed using the procedure date
- If the adverse event month is unknown, then:
 - If the adverse event year matches the year of the procedure date, then impute the month and day using the procedure date
 - Otherwise, assign 'January'
- If the adverse event day is unknown, then:
 - If the adverse event month and year match the month and year of the procedure date, then impute the day using the procedure date
 - Otherwise, assign '01'

For missing data due to patient withdrawal or lost to follow-up in the analyses of time-dependent endpoints, including the primary safety measures, primary performance measure, and secondary measures, the censoring mechanism will automatically account for censored data in the Kaplan-Meier analysis.

7. SUMMARY OF BASELINE INFORMATION

7.1 Patient Enrollment and Accountability

Patient enrollment and disposition including numbers and percentages will be summarized. A patient level listing will also be provided.

7.2 Demographics and Baseline Characteristics

 Edwards	Revision Date: August 22, 2019		Rev	1.0	For Use Only by Affiliates of Edwards Lifesciences	Page 11 of 13
	Title	Statistical Analysis Plan for PASCAL Registry				

Patient demographics, including age, sex, race, are summarized descriptively. Baseline characteristics that describe the disease state and patient condition at baseline are summarized descriptively. The characteristics to be summarized depend on the study indication and measures collected at baseline.

7.3 Medical History and Prior Intervention

Medical history and prior interventions grouped by event types (cardiovascular, cardiovascular intervention and surgeries, and non-cardiovascular) will be summarized by counts and percentages.

7.4 Procedural Information

Procedural information will be summarized including, but not limited to, the type of anesthesia, procedure duration, and the number of implanted devices, by mean and standard deviation for continuous variables and by counts and percentages for categorical variables.

7.5 Baseline Risk Assessments

The following baseline assessments will be summarized by sample size, mean, standard deviation for continuous variable, and counts and percentages for categorical variable.

- STS Risk Score (MV Repair, MV replacement)
- EuroSCORE II
- NYHA Classification

8. STATISTICAL ANALYSIS OF STUDY ENDPOINTS

 Edwards	Revision Date: August 22, 2019		Rev	1.0	For Use Only by Affiliates of Edwards Lifesciences	Page 12 of 13
	Title	Statistical Analysis Plan for PASCAL Registry				

8.1 Primary Safety Measures

The primary safety measure for this study is a composite endpoint of Major Adverse Events (MAEs) at 30 days. No hypotheses testing will be performed for this endpoint. The composite MAE and each individual MAE will be summarized by counts, percentage and 95% Confidence Interval (CI) of the percentage for the ITT and implanted population.

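### SAP 6.2 says Kaplan-Meier censoring handles early loss in the primary safety measure, but SAP 8.1 names a plain percentage with CI, which censors nothing

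*SAP*

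**What the plan says.** SAP 6.2 holds two rules on missing data. The first restricts endpoint analyses, "using only those patients with available data required for endpoint analysis". The second covers withdrawal and loss to follow-up in endpoints it calls time-dependent, "including the primary safety measures, primary performance measure, and secondary measures, the censoring mechanism will automatically account for censored data in the Kaplan-Meier analysis".

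SAP 8.1 says of the primary safety measure: "The composite MAE and each individual MAE will be summarized by counts, percentage and 95% Confidence Interval (CI) of the percentage", in both the ITT and the implanted population. SAP 6.1 says of categorical variables: "If confidence limits are needed, they will be computed using the exact binomial distribution". Its time-to-event convention (Kaplan-Meier estimates at given time points, Greenwood standard errors) is separate, and 8.1 does not invoke it.

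The other endpoint sections do not invoke it either. SAP 8.2 gives counts and percentages by MR grade. SAP 8.3 gives adverse events as counts and percentages, quality-of-life scores and 6MWT as continuous summaries, and NYHA as counts and shifts. SAP 9.1 gives deaths as counts and percentages.

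The parts of a Kaplan-Meier analysis are already in the plan. SAP 5.1.3 notes that "Last Participation Day is used as the censor day for Kaplan-Meier analysis", and SAP 8.3 takes events "with onset on or after the procedure date (Day 0) will be summarized using type of event by early events" and late events by onset day.

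**The concern.** The plan credits its primary safety analysis with a property, censoring, that the named analysis does not have. Whoever programs 8.1 must decide what to do with a patient who leaves event-free before Day 30. Dividing by population N counts that patient as event-free to Day 30. The available-data rule could be read as removing the patient. The censoring sentence would keep the patient at risk until last contact. All three can be defended from the text, and they give different rates from the same data.

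The visit schedule does not settle it. Protocol 4.5 lets the 30-day visit fall anywhere from discharge to 2 months, and SAP 5.2 assigns visits by nominal name even when out of window. A patient seen event-free on Day 10 at a nominal 30-day visit, and never again, could be counted, excluded or censored.

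What is at stake is the reproducibility of the headline safety figure. The registry has no hypothesis test, and no performance goal or comparator is attached to this rate.

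**Working it through.** **No figure to reproduce.** The documents give no expected MAE rate, no loss rate and no precision target. The minimum enrolment of 200 (SAP 2.2) is the only design input. Everything else below is an assumption.

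**Notation.** p = true 30-day MAE probability. c = share of patients whose observation ends before Day 30, independently of their event risk. q = probability that an event falls on or before the day of loss, given that an event occurs.

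**Formulas.**
- Population-N rate: p(1 - c + cq)
- Rate with early-lost, event-free patients excluded: p(1 - c + cq) / [(1 - c) + cpq]

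**Four assumed timing patterns.**
- Half of events on Days 0-3, the rest uniform over Days 4-30; loss at Day 5: q = 0.5 + 0.5 × 2/27 = 0.537
- Same events; loss uniform over Days 4-29 (mean Day 16.5): q = 0.5 + 0.5 × 13.5/27 = 0.750
- Events uniform over Days 0-30; loss at Day 5: q = 6/31 = 0.194
- Events uniform over Days 0-30; loss uniform over Days 4-29: q = 17.5/31 = 0.565

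**Example (p = 10%, c = 5%, q = 0.537).** Population N: 0.10 × (0.95 + 0.02685) = 9.77%. Excluding: 0.09769 / (0.95 + 0.00269) = 10.25%.

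**Range over the four patterns at p = 10%.** The Kaplan-Meier column is the expected Day-30 value from a day-by-day recursion with non-informative loss.

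| Incomplete | Population N | Excluding incomplete | Kaplan-Meier |
|---|---|---|---|
| 2% | 9.84-9.95% | 10.04-10.14% | 10.00% |
| 5% | 9.60-9.88% | 10.09-10.35% | 10.00% |
| 10% | 9.19-9.75% | 10.19-10.74% | 10.00% |
| 20% | 8.39-9.50% | 10.43-11.66% | 10.00% |

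The gap between the two percentages scales with p. At 5% incomplete it is about 0.25 points for p = 5%, 0.5 for p = 10% and 0.7 for p = 15%. At 20% incomplete it is about 1.1, 2.1 and 3.1 points.

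**Check with fixed counts.** Take 20 patients with an MAE, spread evenly over Days 0-29, and 20 of 200 lost event-free before Day 30:
- Population N: 20/200 = 10.0% (exact 95% CI 6.2-15.0)
- Excluding: 20/180 = 11.1% (6.9-16.6)
- Kaplan-Meier, log-log limits: 10.5% (6.9-15.9) if loss is even over Days 1-29, or 10.9% (7.1-16.3) if all loss is at Day 7

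With no early loss, all three point estimates are 10.0%.

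**The case against.** The strongest reply is that the Kaplan-Meier sentence only describes what happens wherever a Kaplan-Meier analysis is run, and that a binomial percentage under 8.1 could sit beside a Kaplan-Meier summary under 6.1. SAP 8.1 does name its populations, which points to population N as the denominator, and it does not rule Kaplan-Meier out. This softens the conflict but does not remove it. The sentence lists the primary safety measures by name, and no endpoint section asks for the estimate. If population N is meant, patients lost early are counted as event-free, which is neither censoring nor an available-data analysis.

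The reply on size largely stands. Observation must stop altogether before Day 30, so a patient who misses the 30-day visit but is seen at one year is complete. Loss of 10-20% by Day 30 is only an assumption. At 2-5% the shifts are a few tenths of a point against a CI of 6.2-15.0%. They are systematic, however, so the CI does not show them.

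A reader might also infer that a patient who dies or has another MAE before the 30-day visit would be dropped for lack of available data. The documents do not support this. No text makes that visit a condition for counting an MAE. Protocol 6 captures events from the procedure until participation ends, SAP 8.3 classes them by onset day, and the date sources in SAP 5.1.2 include "study exit when exit reason is not lost to follow-up, and adverse event occurrence". One clarifying sentence is worth adding, but no bias should be claimed from that reading.

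**Conclusion.** The point holds as a defect of clarity and reproducibility. SAP 6.2 promises censoring for measures that 8.1 to 8.3 analyse by percentages and available-data summaries. For 30-day MAE at an assumed 10% rate, population N reads about 0.1 to 0.4 points low at 5% incomplete and 0.5 to 1.6 low at 20%. Excluding incomplete patients reads about 0.1 to 0.35 and 0.4 to 1.7 points high. Kaplan-Meier returns the assumed rate if loss is non-informative.

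The sizes rest on assumed MAE rates, loss rates and timing. The sign of each error follows from the definitions once some patients are lost early and loss is unrelated to risk. A reader might go further and infer that the registry's safety conclusion is at risk. It is not: the shifts are within sampling error and no decision rule uses the rate. The text should be corrected before analysis because estimation is the registry's whole output.

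**What to change.** In SAP 8.1:
- Name the Day-30 Kaplan-Meier event rate as the headline estimate for the composite MAE and each component, in the ITT and implanted populations. Time events by onset day from Day 0, censor at Last Participation Day (5.1.3) and use the Greenwood-based CI of 6.1.
- For the non-fatal components, state whether death is handled as a competing event or the rate is cause-specific. The composite already includes all-cause death.
- Beside the estimate, give the number of patients with an MAE by Day 30 over population N, and the number followed to Day 30.
- State that follow-up is judged by last participation day, not by the nominal 30-day visit, and that an MAE or death by Day 30 counts as an event whether or not that visit took place.

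In SAP 6.2, limit the Kaplan-Meier sentence to the measures analysed that way. MR grade, quality of life, NYHA and 6MWT are not.

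The cost is SAP wording and a small amount of programming, since the censor day, onset-day classing and Kaplan-Meier conventions already exist. Protocol 8 gives the same general conventions and assigns none to MAE, so nothing there conflicts. There are two downsides. Kaplan-Meier assumes non-informative censoring, which the data cannot confirm. Its CI also widens slightly with loss: in simulated registries of 200 at 10% MAE, with early-clustered events and uniform loss, the mean width was 8.45 points with no loss, 8.51 at 5% incomplete and 8.70 at 20%.
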